7.3.1 End-of-Treatment Disease Evaluation(s)

Disease evaluation is to be performed outlined in Section 7.2.8. within 30 (\pm 3) days of last dose of IP, or before initiating a new antineoplastic therapy, whichever comes first:

Note: If the last radiographic assessment was performed less than 28 days prior to last dose of IP it does not need to be repeated.

For the patients who discontinued treatment for reasons other than disease progression or withdrawal of consent, tumour assessments should be continued and documented every 84 days (± 7 days) until disease progression or initiation of a new antineoplastic treatment (Section 7.4.1).

7.4 Follow-up

7.4.1 Long Term Follow-up

Long-term follow-up assessments will be performed for all patients every 90 (\pm 14) days for 12 months following the EoT visit.

The following information will be collected at each LTFU assessment:

- Patients survival status.
- Subsequent antineoplastic therapies.
- Status of ongoing AEs and/or new treatment-related AEs.

This information may be collected during onsite visits (as part of patients continued treatment at the site), via communication with the patients treating physician or via telephone contact with the patient.

Long-term follow-up will continue until death, withdrawal of consent, or 12 months after the EoT visit, whichever occurs first.

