3.1.2 Secondary Endpoint(s)

- Progression-free survival, defined as the time from inclusion until documented disease progression (PD) according to RECIST v1.1, or RECIST v1.1 combined with biomarker assessment, or IPCG response criteria, or Lugano 5-PS criteria, or death, whichever occurs first.
- Overall survival, defined as the time from inclusion until death due to any cause.
- Best response to treatment according to RECIST v1.1, or RECIST v1.1 combined with biomarker assessment or IPCG response criteria, or Lugano 5-PS criteria, measured at any disease assessment during the course of the study.
- Response duration, defined as the time from first observation of objective response (i.e. PR or CR) according to RECIST v.1.1, or RECIST v1.1 combined with biomarker assessment, or IPCG response criteria, or Lugano 5-PS criteria, until PD or death, whichever occurs first.
- Time to response, defined as the time from inclusion until observation of objective response (i.e. PR or CR) according to RECIST v1.1, or RECIST v1.1 combined with biomarker assessment, or IPCG response criteria or Lugano 5-PS criteria, during the course of the study.
- Frequency and severity of adverse events assessed according to the National Cancer Institute (NCI) Common terminology criteria for adverse events, version 4 (CTCAE v4, Appendix 5).

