3.3 Progression of the Trial

An overview of the different stages of the trial is provided in Figure 2.

Patients participating in the trial will comply with the protocol and receive treatment for a maximum of 24 months (or 52 cycles, whichever is longer), or until disease progression. Treatment may also be terminated early at the initiative of either the patient or the investigator for any reason that would be beneficial to the patient, including: unacceptable toxicity, intercurrent conditions that preclude continuation of treatment, or patient request. Follow-up information (survival, subsequent therapies) will be collected from all patients for 12 months following treatment discontinuation.

A table summarizing the examination/visit schedule is provided in the Section H of the Protocol Synopsis.

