5.4 Treatment Termination

Treatment will be continued for a maximum of 24 months (or 35 cycles, whichever is longer), or until disease progression. Early treatment discontinuation may also occur at the initiative of either the patient or the investigator for any reason that would be beneficial to the patient. These reasons include, but are not limited to: unacceptable toxicity, intercurrent conditions that preclude continuation of treatment, or patient request. The reasons for treatment discontinuation are to be documented in the patient's medical record and reported in the eCRF.

Except in case of consent withdrawal, patient follow-up will continue for 12-months after discontinuation of IP in compliance with the protocol.

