6 EVALUATION OF TREATMENT EFFICACY AND SAFETY

6.1 Efficacy Evaluation

Treatment efficacy will be evaluated in solid tumours by measuring changes in tumour size in response to treatment; measured by computed tomography (CT) scan or Magnetic Resonance Imaging (MRI) according to RECIST v1.1 (Appendix 1). Patients with germ-cell cancer will be evaluated via RECIST v1.1 combined with measurement of biomarkers (AFP, hCG, and LDH; Appendix 2). Patients with PCNSL will be evaluated by magnetic resonance imaging (MRI) according to IPCG response criteria (Appendix 3). For patients with NK/T lymphoma response will be assessed via the 'Lugano' criteria for response assessment using the 5-PS classification system of FDG-PET-CT (Appendix 4 NK/T-cell lymphoma patients with complete response will be further categorised as being in remission or not according to the detectable level of EBV in the blood.

Patients disease will be assessed at "baseline" (during the screening period) and then every 84 ± 7 days until documented PD, or death, whichever occurs first. Assessment of biomarkers in germ-cell cancer patients will be performed on Day 1 of each treatment cycle (after Cycle 1). Patients who discontinue IP treatment for reasons other than progression, death or consent withdrawal will continue to perform disease evaluations every 84 ± 7 days during the LTFU period until PD, or new antineoplastic therapy.

The primary evaluation endpoint is the ORR after the first disease assessment at 84 (± 7) days (i.e. following four cycles of therapy). Death or withdrawal of consent before this point will be considered as treatment failure in this analysis.

Secondary evaluation endpoints include PFS, OS, best response to treatment, time to response and duration of response (see Section 3.1)

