- Median and interquartile range (quantitative variables),
- Survival curve estimates calculated with the Kaplan Meier method (survival data) (Kaplan, 1958).

Each primary and secondary evaluation criterion will be reported with a confidence interval of 95%.

Multivariate predictive analyses of each endpoint will be performed with regression models: logistic regression (for the main end point), and Cox (for PFS and OS) models.

Gail and Simon statistics will be used to test if the disease features and the mutational load measured in tumour samples of certain cohorts is correlated with pembrolizumab efficacy on the primary end point.

Data will be analysed with the SAS (SAS Inc, Cary, NC) and R (https://www.R-project.org/) software packages

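### Survival follow-up stops 12 months after end of treatment, so overall survival is informatively censored beyond about 12 to 15 months

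*Protocol*

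**What the plan says.** Section 3.1.2 gives the endpoint no time limit: "Overall survival, defined as the time from inclusion until death due to any cause". Section 10.2 estimates survival curves by Kaplan-Meier and adds regression with "Cox (for PFS and OS) models".

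Survival status is collected for a limited time only. Section 7.4.1 states: "Long-term follow-up will continue until death, withdrawal of consent, or 12 months after the EoT visit, whichever occurs first". Section 3.3 says: "Follow-up information (survival, subsequent therapies) will be collected from all patients for 12 months following treatment discontinuation". Section 5.4 says that, unless consent is withdrawn, "patient follow-up will continue for 12-months after discontinuation of IP in compliance with the protocol". The synopsis and Sections 3.2 and 7 set a 12-month limit from the EoT visit as well.

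The event that starts this clock is the end of treatment. Section 5.4: "Treatment will be continued for a maximum of 24 months (or 35 cycles, whichever is longer), or until disease progression". Under Section 7.2.8.1, progression found after Day 84 requires withdrawal from treatment whatever the clinical status. The only extension of follow-up, in the synopsis, is up to one further year for rechallenged patients. Under Section 5.5 these must first have completed the full course with clinical benefit.

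No section collects survival for all patients to a common date, although Section 10.1 places the final analysis about 4 years after the last enrolment.

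**The concern.** Kaplan-Meier treats a patient censored at time t as having the same future risk of death as those still followed at t. Under this schedule the patients censored first are those who stopped first, mostly because they progressed. Past about 15 months the curve rests increasingly on patients who progressed late or not at all, and their death rate is applied to everyone. The Cox model for OS needs the same independence, given its covariates, and inherits the problem.

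One secondary objective is to assess efficacy in each cohort in terms of survival. With no control arm, a late OS rate can only be read against outside figures, so a bias in its level passes straight into the interpretation.

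**Working it through.** **1. The plan's own figure.** The protocol states no event count or power for OS. The stated figure that rests on the 12-month limit is the overall duration, about 6.5 years. Inclusion 42 months + treatment 24 + EoT 1 + follow-up 12 = 79 months = 6.58 years. It reproduces, which confirms that the trial is planned around this limit.

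**2. Last survival contact.** Section 7.3 puts the EoT visit 30 (± 3) days after the last dose. Last contact = stop day + 30 + 365, with 30.4375 days per month, counted from first dose. The first scan is the one used for the primary endpoint, "ORR after the first disease assessment at 84 (± 7) days"; the last dose before it is on Day 64.

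| Course | Last contact |
|---|---|
| One dose only | 1 + 395 = Day 396, 13.0 months |
| Progression at Day 84, last dose Day 64 | 64 + 395 = Day 459, 15.1 months |
| Same, counted from the scan | 84 + 395 = Day 479, 15.7 months |
| Progression at Day 168, counted from the scan | 168 + 395 = Day 563, 18.5 months |
| 24-month completer | 730 + 395 = Day 1125, 37.0 months |

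**3. One case worked by formula.** The survival inputs are assumptions, since the protocol gives none. 60% progress at Day 84 (2.76 months). The other 40% have exponential time to progression after that point, median 18 months. Post-progression survival is exponential, median 9 months. Censoring is at progression + 13 months.

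- Hazards: progression λ1 = ln 2/18 = 0.0385; death after progression λ2 = ln 2/9 = 0.0770 per month. Let u = t − 2.76.
- True survival, early group: exp(−λ2·u). Late group, because λ2 = 2λ1: 2·exp(−λ1·u) − exp(−λ2·u).
- At 24 months: 0.6 × 0.195 + 0.4 × 0.688 = 39.2%. At 36 months: 0.6 × 0.077 + 0.4 × 0.479 = 23.8%.
- All early progressors still alive are censored at 2.76 + 13 = 15.76 months. Up to there Kaplan-Meier is correct: 0.6 × 0.367 + 0.4 × 0.845 = 55.8%.
- After 15.76 months only the late group is at risk, without those who progressed more than 13 months ago. The share of the risk set that has progressed is (1 − e^(−13λ1)) / (2 − e^(−13λ1)) = 0.394/1.394 = 0.283, so the observed death hazard is 0.0770 × 0.283 = 0.0218 per month.
- Kaplan-Meier at 24 months: 0.558 × exp(−0.0218 × 8.24) = 46.7%. At 36 months: 0.558 × exp(−0.0218 × 20.24) = 35.9%.

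The bias is about +7.5 points at 24 months and +12 at 36 months. A simulation of the same case gives the same values and no bias at 12 or 15 months.

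**4. Other assumptions.** The first row is a simulated grid on the model of step 3. The others are simulations with progression detected at 84-day visits. Medians are in months; PPS is post-progression survival.

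| Scenario | 24 months | 36 months |
|---|---|---|
| 40–70% early progression, PPS 6–12, PFS of the rest 9–18 | +4 to +9 | +5 to +15 |
| PFS 3, PPS 9, no long responders | +0.6 | +0.8 |
| PFS 6, PPS 12 | +1.9 | +4.4 |
| PFS 3, PPS 9, 15% long responders (PFS 24) | +3.6 | +9.4 |
| PFS 3, PPS 12, 20% long responders | +3.9 | +11.1 |
| PFS 3, PPS 9, shared frailty (log-SD 0.5) | +2.4 | +5.2 |
| PFS 3, steeply falling PPS hazard (Weibull shape 0.5) | −2.2 | −5.7 |
| Same, with 15% long responders | +0.1 | +1.6 |

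Entries are Kaplan-Meier minus true OS in percentage points. The visit-based runs show no bias up to 15 months. Patients who stop before the first scan can leave follow-up somewhat earlier, hence the lower limit of about 12 months.

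**5. After the change.** With one cut-off at the final analysis, every patient has at least about 48 months of potential follow-up. Censoring then depends on entry date alone, so Kaplan-Meier is unbiased through 36 months when entry date is unrelated to prognosis.

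**The case against.** The strongest reply concerns size and consequence. A reader might infer that OS is certain to be overstated by a known amount. The documents do not support that: they give no PFS or post-progression assumption for any cohort, and seven different diseases will not share one. The large figures come from an assumed mix of early progressors and long responders; with one short PFS distribution the bias is about 1 point, and it can be negative. This stands, and the direction has to be stated as expected, not certain.

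It can also be said that OS drives no decision, that the protocol names no 24- or 36-month rate, and that precision is poor anyway. At a 24-month OS near 39%, the 95% half-width is 1.96 × √(0.39 × 0.61/n), about 14 points for n = 50 and 21 for n = 20, before any censoring. That limits the practical weight. It does not remove a systematic error, which the reported interval would not reflect.

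Last, truncation or weighting could be left to the SAP, which is not shown. True, but no SAP can recover survival status that the protocol stops collecting. Weighting would also have little to work with, because past about 16 months almost nobody who progressed at the first scan remains under observation.

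**Conclusion.** The point holds in conditional form. The protocol's follow-up rule ties OS censoring to the end of treatment, and so mainly to progression. Kaplan-Meier and Cox analyses of OS are therefore informatively censored beyond about 12 to 15 months. The mechanism follows from the text alone; the size rests on the assumed survival inputs above. A mix of early progressors and a minority with long benefit is what the trial sets out to find, and in that mix the bias is material. The rechallenge extension lengthens follow-up only for patients with prior benefit, so it widens the imbalance.

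Two further inferences should be resisted. The finding does not touch the primary endpoint or the stopping rules, which use early response (with disease stabilisation also counted in the ovarian cohort). Nor is 13 months a safe limit for everyone: Section 7.3 allows the EoT visit earlier than 30 days if a new antineoplastic therapy starts, and Sections 3.3 and 5.4 count from treatment discontinuation. About 12 months is the defensible limit.

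**What to change.** **Preferred.** Amend Section 7.4.1, and the matching text in the synopsis and Sections 3.2, 3.3, 5.4 and 7, so that survival status is collected for every patient who has not withdrawn consent up to one common calendar cut-off. Censor OS administratively at that date. Section 7.4.1 already allows this information to be obtained by telephone or from the treating physician, so no new procedure is needed. The cost is an amendment and a few extra vital-status contacts per surviving patient.

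**Fallback.** If collection stays as it is, limit Kaplan-Meier and Cox summaries of OS to about 12 months and say why. This needs only analysis wording, but it has a real price: no late OS is reported, including for the long responders whom the trial hopes to identify.

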7.4.2 Efficacy follow-up

All patients who discontinue treatment for reasons other than disease progression, or withdrawal of consent from the entire study should continue to be assessed every 84 (\pm 7) days during the LTFU period to monitor disease status, until disease progression or initiation of a new antineoplastic treatment or death.

The disease evaluation will be performed according to the methods outlined in Section 7.2.8.

7.4.3 Second Course assessments

Second course assessments will be performed for only the eligible patients rechallenged with pembrolizumab (See Section 5.5) every 90 (± 14) days for 12 months in the same way as for the LTFU.Prior to the first re-administration of pembrolizumab, the following parameters will be checked by the investigator

- Inclusion/non-inclusion safety criteria
- Radiographic disease progression assessed by RECIST 1.1 for patients with solid tumours, RECIST v1.1 combined with biomarker assessment for patients with germ-cell cancer, the IPCG response criteria for patients with PCNSL, the 'Lugano' criteria for response assessment using the FDG-PET-CT 5-PS and assessment of EBV load for patients with NK/T Lymphoma.
- Negative urine or serum pregnancy test for women of childbearing potential.

The following information will be collected:

- Written informed consent,
- Patients' survival status and disease status,
- Status of ongoing AEs and/or new treatment-related AEs.

This information will be collected during onsite visits.

The second pembrolizumab course will continue until 12 months of retreatment, disease progression or until the end of the study, whichever occurs first.

During the second course, pembrolizumab will be administered and managed in the same way as the initial course, according to the Investigator Brochure and all the guidelines outlined above in section 5.

7.5 Provisions in Case of Treatment or Trial Interruption

In cases of patient withdrawal of consent or early trial termination, all efforts should be made to perform the EoT visit assessments (see Section 7.3). The patient's future clinical management will be left to the discretion of the treating physician

8 SAFETY EVALUATION

8.1 Adverse Events

8.1.1 General definition

An adverse event is defined as any untoward medical occurrence, in a patient or clinical trial subject treated by a medicinal product and which does not necessarily have a causal relationship with this treatment. An AE can therefore be any unfavourable and unintended sign (including an abnormal laboratory finding, for example), symptom, or disease temporally associated with the use of a medicinal product or protocol-specified procedure, whether or not considered related to the medicinal product or protocol-specified procedure. Any worsening (i.e., any clinically significant adverse change in frequency and/or intensity) of a preexisting condition that is temporally associated with the use of the investigational product, is also an AE.

Changes resulting from normal growth and development that do not vary significantly in frequency or severity from expected levels are not to be considered AEs.

Progression of the disease under study is not considered as AE.

All subjects will be monitored for AEs during the study. Assessments may include monitoring of any or all of the following parameters: the subject's clinical symptoms, laboratory, pathological, radiological or surgical findings, physical examination findings, or findings from other tests and/or procedures.

8.1.2 Evaluating Adverse Events

As far as possible, each AE should be evaluated to determine:

- The severity of the event
- Its relationship to the IP (related/ not related)
- Its duration (start and end dates or if continuing at final exam)
- Action taken (corrective treatment, hospitalization/prolonged hospitalization, ...)
- The seriousness of the event (Section 8.2).

Severity

The severity (intensity) of AEs must not be confused with the seriousness criterion which is the guide for defining the reporting requirements (Section 8.2). Severity will be assessed by a qualified physician (Investigator) using the NCI CTCAE version 4.0 (Appendix 4). The intensity of adverse events not listed in this classification will be assessed according to the following qualifiers:

- **Grade 1**: **Mild**; asymptomatic or mild symptoms; clinical or diagnostic observations only; intervention not indicated.
- **Grade 2**: **Moderate**, minimal local or noninvasive intervention indicated; limiting age-appropriate instrumental activities of daily living (ADL).
- **Grade 3**: **Severe** or medically significant but not immediately life-threatening; hospitalization or prolongation of hospitalization indicated; disabling; limiting self-care ADL.
- Grade 4: Life-threatening consequences; urgent intervention indicated.
- Grade 5: Death related to the event.

Relationship

The investigator must do his/her best to explain each adverse event and establish when it exists, the connection with the IP.

Duration

Adverse events must be followed until they have resolved or stabilized.

8.1.3 Adverse Event Reporting

All AEs that occur from the time the informed consent form is signed until 30 days after the last dose of IP must be reported by the Investigator (the reporting timeframe for AEs meeting any serious criteria is described in Section 8.2). All AEs will be recorded on the AE page of the CRF and in the subject's source

UNICANCER

documents. The investigator will make every attempt to follow all subjects with non-serious AEs for outcome.

8.2 Serious Adverse Events

8.2.1 General definition

A serious adverse event is defined as any untoward medical occurrence or effect that at any dose:

- results in death,
- is life-threatening,
- requires hospitalization or prolongation of existing hospitalization,
- results in persistent or significant disability or incapacity,
- is a congenital anomaly or birth effect,
- or is medically relevant in the context of the pathology and the clinical trial.

These characteristics/consequences have to be considered at the time of the event. For example, regarding a life-threatening event, this refers to an event in which the subject was at risk of death at the time of the event; it does not refer to an event which hypothetically might have caused death if it was more severe.

The terms disability and incapacity correspond to any clinically relevant physical or psychic handicap, transient or permanent, with impacts on the physical condition/activity and/or the quality of life of the patient.

Medical and scientific judgment should be exercised in deciding whether other situations should be considered serious, such as important medical events that might not be immediately life-threatening or result in death or hospitalization, but might jeopardize the patient or might require intervention to prevent one of the other outcomes listed in the definition above (for example: overdose, second cancer,...).

The following events leading to a hospitalization or prolongation of hospitalization are not considered as Serious Adverse Events:

- Hospitalisation already scheduled before the start of the trial,
- Hospitalisation required as part of the protocol (biopsy, chemotherapy, etc.),

Any SAE, or follow up to a serious adverse event (including death due to any cause other than progression of the cancer under study) that occurs from the time the informed consent form is signed until 28 days after the last dose of IP must be reported to the Sponsor within 24 hours of the Investigator's knowledge.

Additionally, any SAE which is considered to be related to the study treatment by an investigator which occurs at any time outside of the time period specified in the previous paragraph also must be reported immediately to the Sponsor.

All subjects with serious adverse events must be followed up for outcome.

The assessment of whether there is a reasonable causal relationship is made by the investigator. If the sponsor disagrees with the investigator's causality assessment, the opinion of both the investigator and the sponsor should be provided with the report.

